3. STUDY DESIGN AND PROCEDURES

3.1 Overall study design and flow chart

This is a prospective, randomized, controlled, open clinical study with parallel-group design. A total of 70 young males with delayed or absent puberty will be randomized to receive hormone replacement during 6 or 12 months. The study includes 9 or 10 visits at the clinic during a total period of 12 months.

To not expose boys for a new treatment (Nebido and Puregon in group I and Nebido in group II) that is inferior to Stand of Care Testoviron, a fertility test will be performed after 10 evaluable patients in each arm in the groups.

The subjects will be divided to two groups depending on whether they have I) absences of puberty (n=30) or II) delayed/slow progress of puberty (n=40):

I) Boys with absence of puberty (testis 1-3 mL and morning testosterone less than 0.5nM) will be randomized to two alternative pubertal replacement therapies; 1) low dose of Testoviron Depot® (SoC) 50 mg i.m. injection once a month or 2) rhFSH (Puregon®) and low dose Nebido® (one injection of 200 mg every 3 months). Those randomized to receiving rhFSH (Puregon®) and low dose Nebido® will start both treatments concomitant. The rhFSH (Puregon®) dose will be adjusted to reach serum FSH levels of 3-5IU/ml (see appendix D). This is expected to happen within one month (first check after one week after start of treatment with Puregon) and if not reach within one month of start of Puregon treatment the patient will be withdrawn from the study. Boys who have been randomized to Puregon/Nebido but at inclusion have serum levels of FSH above 3 will not be treated with Puregon, but if the patient during the study on 2 concomitant visits have serum FSH below 3IU/L he will be treated with Puregon to achieve serum FSH levels 3-5 IU/L during the rest of the study (see appendix D). The treatment will continue for 12 months. The effect will be evaluated after 6 and 12 months respectively on the development of masculinization and on spontaneous start of puberty. If the spontaneous puberty has started, the pubertal hormone replacement treatment will be stopped. The Nebido treatment will be dose adjusted in patients after the 1st injection if the testosterone profile shows to high or low levels; the goal is to have similar levels during 2 months as in early puberty (1-3 nM). For individual Nebido® adjustments in group I see appendix D.

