3.1.1 Stopping criteria

To avoid that the treatment with Nebido and Puregon in group I and Nebido in group II is not inferior to SoC, a futility test will be performed after 10 evaluable patients in each arm in the groups. This futility analysis can result in stopping the study if the new treatment (Nebido and Puregon in group I and Nebido in group II) is statistically significant inferior or superior, or continue the study as planned or increase the numbers patients to have a possibility to reach statistical significance.

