4.6 Withdrawal of subjects and study stop

Subjects are free to discontinue their participation in the study at any time without prejudice to further treatment. The subjects may be withdrawn from the study at the discretion of the investigator due to safety concerns or if judged non-compliant with study procedures. Other reasons for discontinuing a subject are incorrect enrolment and subjects lost to follow-up.

A subject who discontinues will be asked about the reason(s) for discontinuation and the presence of any adverse events. If possible, they will be seen and assessed by the investigator. Adverse events will be followed up.

Also, the manufacturers of the study drugs may revoke their products, which may lead to the entire study may be interrupted.

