6.3 LHRH-test

The LHRH-test will be performed in the Group I subjects at visits 1, 8 and 10.

At visit 8 (after 6 months) the LHRH-test will be performed in the morning, before the first Nebido injection is given. In the Testoviron- arm, the LHRH-test will be made same day as Testoviron administration but prior to the injection itself.

At visit 10 (after 12 months) the LHRH-test will be performed same day as the Nebido/Testoviron injections but prior to the injection itself.

The LHRH-test involves injecting synthetic LHRH into a vein and measuring blood for LH and FSH levels (which, if the pituitary is functioning normally, will rise). A blood sample is taken before the injection, then 20 and 60 minutes afterwards. A cannula is placed in a vein in the arm to enable the nurse to give the LHRH and take samples. Side-effects are rare, but can include nausea, headache and flushing.

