8. STATISTICAL METHODS AND SAMPLE SIZE

The aim of this hypothesis-generating study is to evaluate the development of puberty in young males with a delayed progress or absent puberty after various testosterone supplementations with or without rhFSH. The primary endpoint of this study is pubertal LH responses on GnRH test at 12 months (group I) and testis size 8 mL or more for young males with a delayed progress puberty (group II). LH ≥ 1 ug/mL is clinically relevant sign that puberty has started and 8mL in testis size relevant for the clinical signs of puberty (growth spurt). The primary endpoint is in both groups a dichotomy response (0/1 yes or no).

The sample size is not formally calculated with consideration to statistical power since Testoviron treatment is SoC today and has not been evaluated.

Since one of the aims in the study is to know if Testoviron treatment can be replaced by Puregon/Nebido in boys with ascents of puberty and by Nebido in boys with delay and slow progression of puberty a bioequivalence analysis and non-inferior interpretation will be performed on primary end points.

Bioequivalence analysis and Non-inferior interpretation: The new treatments will be clinically considered similar if the treatments are in 80 -125 % of the result of Testoviron in each group. Since the result on the primary endpoint cannot be expressed with confidence interval (the result on the primary end point is yes or no), the statistical analysis of the results will be done with Fisher exact chi-square test. Furthermore, accepting a criterion that the difference of numbers of boys becoming pubertal being at the most 25%, and further assuming, that 80% (p2, n=16) boys on the old drug, Testoviron Depot®, will become pubertal: using the normal approximation when calculating the lower 95% level for the difference between p1 (% success for boys on Nebido®) and p2 (80%), the number of boys becoming pubertal on Nebido® must exceed 15." (see Appendix E).

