- a. The rhFSH (Puregon®) dose will be adjusted to reach serum FSH levels of 3.0 IU/mL or higher. The starting dose will be 50 IU. The FSH levels will be determined on visit 4. If serum FSH is lower than 3.0 IU/L the dose will be increased to 75 IU. If serum FSH are higher than 5.0 IU/L the dose will be reduced to 30 IU. Patients who have changed the Puregon® to 30IU or 75IU, an extra visit 7 -10 days after the change will be done to determine the serum FSH levels. For patients on 75IU Puregon® if serum FSH under 3.0 IU/L the Puregon® dose will be increased to 100IU and if serum FSH are higher than 5.0 the dose will be reduced to 50IU. For patients on 30IU Puregon® if serum FSH under 3.0 IU/L the Puregon® dose will be increased to 50IU and if serum FSH are higher than 5.0 the treatment with Puregon® will be stopped. If serum FSH in these patients are not 3.0 IU/mL or higher at visit 5, the patient will be taken out from the study.
- b. Dose adjustments of starting dos of Puregon® is possible after the first 5 patients for the rest of the study. If the serum FSH levels are less than 3.0 IU/L at visit 4 in 3 or more of 5 patient, the starting dose will be increased to 75IU for the remaining patients randomized to Puregon® and Nebido®.
- c. Boys who have been randomized to Puregon®/Nebido but at inclusion have serum levels of FSH above 3 will not be treated with Puregon®, but if the patient during the study on 2 concomitant visits have serum FSH below 3.0 IU/L will be treated with (Puregon®) as described above
- d. The Nebido treatment will be dose adjusted in patients after the first injection if the testosterone profile shows to high or low levels, the goal is to have the similar levels during 2 months as in early puberty (1-3 nM). If the serum testosterone level are less than 1.0 nM at visit 6, the dose will be increased to 250mg for the remaining part of the study. If the serum testosterone level is higher than 3.0 nM at visit 6, the dose will be decreased to 150mg.

II Boys with delayed/slow progress of puberty

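### In Group I, boys who miss an FSH target on Puregon leave the study at about one month; the rule exists in one arm only, and the plan does not say how they count at 12 months

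*SAP*

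**What the plan says.** **Removal rule.** Section 3.1 sets the Puregon target ("dose will be adjusted to reach serum FSH levels of 3-5IU/ml") and adds that "if not reach within one month of start of Puregon treatment the patient will be withdrawn from the study". Appendix D (I a) gives the target as "dose will be adjusted to reach serum FSH levels of 3.0 IU/mL or higher" and the consequence as "If serum FSH in these patients are not 3.0 IU/mL or higher at visit 5, the patient will be taken out from the study". Both refer to the study, not only to treatment. Section 5.1.1 gives Testoviron at a fixed dose, and no biomarker-based removal is stated for that arm.

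**Endpoint.** Section 8: "The primary endpoint of this study is pubertal LH responses on GnRH test at 12 months (group I"), scored 0/1. Section 6.3: "The LHRH-test will be performed in the Group I subjects at visits 1, 8 and 10". These are baseline, 6 months and 12 months.

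**Boys who discontinue.** Section 4.6 asks for the reason and any adverse events, which are followed up. Beyond that: "If possible, they will be seen and assessed by the investigator".

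**Analysis.** Section 8 and Appendix E name Fisher's exact test and a 25% criterion. They name no analysis set and no rule for a missing 12-month result. Section 3.1.1 says "a futility test will be performed after 10 evaluable patients in each arm in the groups", without defining evaluable. Section 9.1 leaves the reasons for excluded data to the study report.

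**The concern.** Removal happens after randomisation, in one arm only, and depends on how the boy responds to the new drug. Removal is at visit 5 (1 month) and the next LHRH test is at visit 8 (6 months), so a removed boy has no outcome under the plan. Omitting him is the natural reading of withdrawal from the study and of an evaluable patient, but the plan does not state it.

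The direction of the effect depends on who is removed and how they are counted:

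- Omitted, and poorer responders than the rest: the comparison is biased towards Puregon/Nebido.
- Omitted, and no different from the rest: no shift is expected.
- Scored 0, and no different from the rest: the comparison is biased against Puregon/Nebido.

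Section 8 uses this endpoint to judge whether Puregon/Nebido can replace Testoviron. Section 3.1.1 allows the study to stop on the look at 10 per arm. The study is open, so a counting rule chosen late could be chosen with the results in view. A 12-month test that was never done cannot be recovered.

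**Working it through.** **1. The plan's own figure (Appendix E, 20 per arm, Testoviron 16/20).** Lower limit = (p1 − p2) − z·√[p1(1−p1)/20 + p2(1−p2)/20].

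- 16/20: 0 − 1.96 × 0.126491 = −0.248, inside −0.25.
- 15/20: −0.05 − 1.96 × 0.131814 = −0.308, outside.
- With z = 1.645 the limits are −0.208 and −0.267.

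The stated threshold of 16 reproduces with either z, so the plan's lower 95% level fits both.

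**2. Can one boy decide the result in Group I?** Table 2 gives 15 per arm. Suppose 12/15 succeed in each arm.

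- All boys: SE = √(0.16/15 + 0.16/15) = 0.1461; limit = 0 − 1.96 × 0.1461 = −0.286, criterion failed.
- One removed non-responder omitted, 12/14 = 0.857: SE = √(0.857 × 0.143/14 + 0.16/15) = 0.1393; limit = 0.057 − 1.96 × 0.1393 = −0.216, criterion met.

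**3. Chance of wrongly passing.** This is an exact enumeration over both binomial distributions.

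- Inputs: 15 per arm; Testoviron 80% (section 8, worked there for 20 per arm, the Group II size); margin 25 points.
- The new arm is set on the margin at 80 − 25 = 55%.
- Pass if the lower limit exceeds −0.25.
- Assumption: 1, 2 or 3 boys removed. The documents give no rate.
- Where a range is shown, the lower value removes k certain failures and leaves the other boys at 8.25/(15 − k), with 8.25 = 15 × 0.55. The upper value removes up to k of the failures that occur.

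| Handling, z = 1.96 | 1 boy | 2 boys | 3 boys |
|---|---|---|---|
| All 15 analysed with their outcomes | 2.9% | 2.9% | 2.9% |
| Would-be failures omitted | 4.8–5.5% | 9.4–11.7% | 14.4–18.5% |
| Omitted boys had 30% success | 3.6% | 5.4% | 6.4% |
| Unrelated to outcome, omitted | 2.9% | 3.3% | 2.9% |
| Unrelated to outcome, scored 0 | 1.3% | 0.5% | 0.2% |

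With z = 1.645 the all-boys figure is 5.5%. Omitting 1, 2 or 3 would-be failures gives 8.4–9.2%, 15.1–17.3% and 21.7–24.9%.

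For other Testoviron rates, with the new arm 25 points lower, two failures omitted and z = 1.96: 4.8–5.1% at 50%, 6.3–7.4% at 70% and 16.8–20.8% at 90%.

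**4. Fisher's test.** It does not test the margin. Under the same 80% v 55%, its chance of showing the new arm significantly lower (two-sided p < 0.05) is 17.0% with all boys. With 1, 2 or 3 would-be failures omitted it is 16.5–17.0%, 11.1–12.2% and 5.2–6.9%.

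**5. The removal criterion, side by side.**

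| Place | FSH criterion |
|---|---|
| Section 3.1, at start | 3–5 IU/ml |
| Section 3.1, later starters | 3–5 IU/L |
| Section 5.1.1, later starters | 3–6 IU/L |
| Appendix D | 3.0 IU/mL or higher; titration limits 3.0 and 5.0 IU/L |

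A boy on 30 IU with FSH above 5.0 is outside the section 3.1 range. Appendix D stops his Puregon and does not remove him. Section 3.1 also counts one month from the start of Puregon while Appendix D fixes visit 5; these differ for a boy who starts later.

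**The case against.** **Few boys may be removed.** Boys with FSH above 3 at inclusion start without Puregon. Appendix D titrates the dose, adds an FSH visit after a change, and can raise the starting dose for later boys. This stands: the number could be zero, and then nothing shifts. But Appendix D itself plans for 3 or more of the first 5 boys being below 3.0 at visit 4, and step 2 shows that one boy can be enough.

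**The larger error rates need every omitted boy to be a failure.** This stands. No section links FSH at one month to LH response at 12 months, and with milder assumptions the effect is small or absent. How many boys miss the target, and how they would have done, are not things a plan can fix. Follow-up and the counting rule are.

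**The FSH texts can be read together.** On this reading, boys are titrated to 3–5 and removed only below 3, a lower bound that all the passages share. That is reasonable and makes this part secondary, but the passages still differ in range, unit and timing.

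**Scoring missing tests as 0 is costly.** This stands. If both arms truly succeed at 80% and removal is unrelated to outcome, the chance of passing (15 per arm, z = 1.96) falls from 46% to 28%, 13% or 4% with 1, 2 or 3 boys scored 0. It matters little if the 12-month test is obtained.

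**The study is called hypothesis-generating.** Section 8 nevertheless announces a non-inferiority reading of the primary endpoints, and section 3.1.1 attaches stopping to the early look.

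**Conclusion.** The concern holds and should be fixed before the Group I comparison is relied on. The plan removes randomised boys from one arm for a response measured after randomisation, provides no 12-month outcome for them, and does not say how they count. That much follows from the text without assumptions.

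The direction and size of any bias are not established. In the cases worked at 80% v 55% with z = 1.96, the chance of wrongly passing ranges from 0.2% to 18.5%, against 2.9% with all boys analysed. Where it falls depends on an unknown number of removals, on how those boys would have done, and on an 80% Testoviron rate borrowed from the 20-per-arm working. The differing FSH criteria are a lesser point, but they bear on who is removed.

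**What to change.** - **Section 3.1 and Appendix D:** separate stopping study treatment from leaving the study. A boy who misses the FSH target stays in follow-up, with the visits already planned and the 12-month GnRH test. His treatment remains a clinical decision, which the sponsor should state.
- **Section 8:** make the primary analysis all randomised boys in their assigned arm, and use the same set at the look at 10 per arm in place of undefined evaluable patients.
- **Section 8:** state in advance one rule for a missing 12-month test, the same in both arms. Counting it as not pubertal, with a sensitivity analysis, is one example. Report the subset reaching the FSH target only as a sensitivity analysis.
- **Sections 3.1 and 5.1.1 and Appendix D:** reconcile the FSH criterion, its units and its timing.

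The cost is a short amendment to sections 3.1, 5.1.1, 8 and Appendix D. It adds no visit or test to those already planned for each boy. The response rate in the new arm may be lower, and the chance of passing falls if tests go missing and count as failures, so effort should go into obtaining the 12-month test.

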3.1.1 Stopping criteria

To avoid that the treatment with Nebido and Puregon in group I and Nebido in group II is not inferior to SoC, a futility test will be performed after 10 evaluable patients in each arm in the groups. This futility analysis can result in stopping the study if the new treatment (Nebido and Puregon in group I and Nebido in group II) is statistically significant inferior or superior, or continue the study as planned or increase the numbers patients to have a possibility to reach statistical significance.

3.1.1.1 Stopping criteria for dose continuation

General stopping criteria for dose continuation are hypersensitivity reactions to the active substance or any excipients. However, mild skin reaction at the injection- or patch site will not be judged as stopping criteria.

The first dose of Puregon will be given at the clinic under medical supervision for approximately 2 hours to exclude any acute hypersensitivity reaction. Acute toxicity of Puregon is very low. No special treatment measures are required in case of overdose except that drug treatment should be stopped or the dosage reduced.

Suspected anaphylactic reactions have been reported after injection of Nebido. Subjects will be observed after each injection at the clinic and in case of any reaction routine medical care applies.

3.2 Rationale for study design, doses and control groups

The research group have clinical experience on testosterone levels from a few patients who have successfully been treated with Nebido at Swedish hospitals (unpublished data). This is the base for the chosen doses in the present study. The dose of Testoviron Depot® is the off-label dose most commonly used in Sweden.

This study is open (not blinded) and does not use placebo-control design. It would not be, according to our view ethical acceptable to decline young males hormone replacement therapy in a placebo-controlled study design since the inclusion exclusion criteria are similar to the requirement in clinical routine in the Department of Pediatrics at the NÄL-hospital in Trollhättan and SU/Östra in Göteborg to obtain treatment. Every year during the relatively short period of puberty is valuable for the young males to receive treatment. Recruitment of subjects into this study will be among boys who actively

seek medical care for worries about delayed puberty. The psychological consequences of pubertal delay in boys are noteworthy because it involves emotional distress, poor body image and low self-esteem (4). These boys are also more likely to be teased or bullied. Mood and anxiety disorders are among the most prevalent mental health conditions affecting youth, boys as well as girls. Boys may be more reluctant to seek care for emotional problems, fearing that this may be perceived as a weakness. Therefore, it is of utmost importance for the clinician to bring up these topics with young men.

To not expose boys for a new treatment (Nebido and Puregon in group I and Nebido in group II) that is inferior to SoC, a futility test will be performed after 10 evaluable patients in each arm in the groups. This futility analysis can result in stopping the study if the new treatment (Nebido and Puregon in group I and Nebido in group II) is statistically significant inferior or superior, or continue the study as planned or increase the numbers patients to have a possibility to reach statistical significance.

4. SUBJECT POPULATION

A total of 70 young healthy males between 14 and 16 years with clinically verified absent or delayed puberty will be included. The study population will be identified among referrals to the Department of Pediatrics at the NÄL-hospital in Trollhättan and SU/Östra in Göteborg.

Subjects will be divided into 2 main groups; Group I and Group II depending on puberty status. Each group will be sub-divided into treatment groups (Table 2):

Table 2 *Subjects and treatment*

Subjects	Treatment	N
Group I (absent puberty):	1) Testoviron	15
	2) Puregon and Nebido	15
Group II (delayed puberty):	1) Testoviron	20
	2) Nebido	20

Investigator must keep a record of subjects who entered pre-study screening but were never enrolled (subject screening log). Subjects that do not meet the inclusion/exclusion criteria for a study must not be enrolled into the study. Subject population should be selected without bias.

Two groups of boys will be included; Group I with absent puberty and Group II with delayed puberty

4.1 Inclusion criteria Group I (absent puberty)

For inclusion in the study subjects must fulfil the following criteria.

1. Signed informed consent

2. Healthy young male subjects 14-16 years old
3. Morning serum testosterone value by inclusion (07.30-09.00) and start (08.00-10.00) that is less 0.5 nmol/L
4. Pre-pubertal LHRH test
5. Testicular volume 1-3ml bilaterally
6. Bone age 11 years or older
7. Otherwise clinically normal physical findings and laboratory values as judged by the investigator

4.2 Inclusion criteria Group II (delayed puberty)

For inclusion in the study subjects must fulfil the following criteria.

1. Signed informed consent
2. Healthy young male subjects 14-16 years old
3. Morning serum testosterone by inclusion (07.30-09.00) of 1 – 3 nmol/L and at start (08.00-10.00) less than 4 nmol/L
4. Testicular volume 4-6 mL bilaterally
5. Bone age more than 11 years or older

4.3 Exclusion criteria

Subjects must not enter the study if any of the following exclusion criteria are fulfilled

1. Growth spurt
2. Bone age < 11 years
3. Untreated hypothyroidism
4. Suspected growth hormone deficiency
5. Untreated celiac disease
6. Steroid or immune-suppression medicated disease
7. Training doses over 10 hours a week
8. Known or suspected allergic reaction towards the active substances or other components
9. Clinical judgement by the investigator that the subject should not participate in the study
10. Use of anabolic steroids or other drugs.

Subjects that do not meet the inclusion/exclusion criteria for a study should not, under any circumstances, be enrolled into the study.

4.4 Subject enrolment and randomization

The investigator will obtain signed informed consent from the potential subject as well as both parent(s)/guardian(s) before any study specific procedures are performed. The investigator will thereafter determine subject eligibility according to study criteria and finally assign eligible subject unique *randomization code* (i.e. subject number).

Randomization codes will be assigned strictly sequentially as subjects are eligible for randomization. If a subject discontinues participation in the study, his subject number cannot be re-used. New subject gets a new number in consecutive order.

A randomisation schedule, containing randomisation code and treatment, will be provided by one of the study leaders.

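### Section 4.4 does not keep the next treatment from those who recruit in this open trial, and does not say that the schedule is blocked or separate for Groups I and II

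*SAP*

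**What the plan says.** SAP section 4.4 sets out the allocation steps. After consent, "The investigator will thereafter determine subject eligibility according to study criteria and finally assign eligible subject unique" randomisation code. On order it states: "Randomization codes will be assigned strictly sequentially as subjects are eligible for randomization". On the list it states: "A randomisation schedule, containing randomisation code and treatment, will be provided by one of the study leaders". A number is not re-used after a boy discontinues; the next boy takes the next number.

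Section 3.2 says of masking: "This study is open (not blinded) and does not use placebo-control design". Section 4.3, item 9, lets the investigator exclude a boy on this ground: "Clinical judgement by the investigator that the subject should not participate in the study". Section 5.1.2 puts both the randomisation code and the product name on the drug label.

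Sections 3.1 and 4 (Table 2) plan 70 boys: 15 per arm in Group I and 20 per arm in Group II. Sections 3.1.1 and 8 place a futility look after 10 evaluable boys in each arm of each group.

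**The concern.** Concealment matters most where treatment is open and entry involves judgement. If the person deciding on a boy's entry knows which treatment comes next, he can enter, defer or decline the boy in that light, knowingly or not. Randomisation then no longer guarantees comparable arms.

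Group II shows what is at stake. Boys enter at 4 to 6 mL (section 4.2) and succeed at 8 mL or more (section 2.1.1), so a boy at 6 mL starts closer to success than one at 4 mL. The primary analysis is a Fisher test without baseline adjustment (section 8), and the non-inferiority rule in Appendix E turns on a single boy, as shown in the working.

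The structure of the list is a second, smaller question. Table 2 fixes equal arms within each group and the futility look counts boys per arm within each group, but section 4.4 does not say how the schedule delivers this.

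**Working it through.** **Planned sizes.** Table 2 adds up: 15 + 15 = 30, 20 + 20 = 40, and 30 + 40 = 70. There is no power-based sample size to reproduce.

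**Concealment.** This part rests on reading the sections together.

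- Who decides entry: the investigator (4.4), with discretion under 4.3 item 9.
- Who gives the code: the same investigator, afterwards (4.4).
- In what order: strictly sequential (4.4).
- What the schedule holds: code and treatment (4.4).
- Who supplies it: one of the study leaders (4.4), not stated to be outside recruitment.
- What withholds the next treatment: nothing stated. No envelopes, central release, third-party holder or limit on access appears in any section.

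With a fixed sequence, anyone who has seen the schedule knows the next treatment with certainty, against a 50% guess under concealed 1:1 allocation.

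**How little selection could matter.** Appendix E takes 20 boys per arm, 16 successes on Testoviron Depot and a margin of 25 percentage points. The lower limit is (p1 − p2) − 1.96 × √[p1(1 − p1)/20 + p2(1 − p2)/20].

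- 16 successes on the new drug: 0 − 1.96 × 0.126491 = −0.248, inside the margin.
- 15 successes: −0.05 − 1.96 × 0.131814 = −0.308, outside it.

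One boy's outcome changes the conclusion. This shows how sensitive the rule is; it does not estimate the bias.

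**List structure.** The plan states neither the type of list nor any block size, so each line below is an assumption. Where one list serves both groups, the 30 Group I boys are taken to fall at random positions among the 70.

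- One list balanced 35:35: P(15:15 in Group I) = C(35,15) × C(35,15) / C(70,30) = 0.191. Group II is then 20:20 as well. P(18:12 or more uneven in Group I) = 0.227.
- Simple 1:1 randomisation: P(15:15) = C(30,15)/2^30 = 0.144; P(20:20) = C(40,20)/2^40 = 0.125; both = 0.144 × 0.125 = 0.018.
- One list in blocks of 2, 4 or 10, not separated by group (simulation, 60,000 runs each): both splits exact in 19.3%, 12.9% and 19.3%.
- A separate blocked list per group, closing at 30 and 40: both splits exact if all planned boys are enrolled.

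**What an uneven split costs.** With equal variance per boy, the variance of a difference at 18:12 relative to 15:15 is (1/18 + 1/12) / (2/15) = 0.1389 / 0.1333 = 1.04, a loss of about 4%.

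**The case against.** The strongest reply is that section 4.4 is silent rather than wrong. It does not say that the enrolling investigator holds or sees the schedule, and every randomisation schedule contains code and treatment. A reader might infer that the recruiter works with the open list in front of him; the text does not say so. What remains is that 4.4 fixes who assigns, in what order and from whose list, and puts no barrier in between. The document is headed as the clinical study protocol and 4.4 is its randomisation section, so the barrier belongs there.

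A reader might also infer that one run of codes serves both groups. The documents do not support this as a fact. Section 3.1 describes randomisation within each group, the new-treatment arms differ between groups, and group-specific lists may well be intended. This objection stands, and the probabilities above are therefore conditional.

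There are partial safeguards. Section 4 requires a log of boys screened but not enrolled and selection without bias. Most entry criteria are measured, section 9.3 provides monitoring, and strict sequence itself prevents choosing among codes. These measures can discourage or expose selective entry, but they do not conceal the next treatment.

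Finally, a reader might conclude that no analysis could repair the damage. That goes too far: testis size is recorded at visit 1 (section 6.4), so imbalance in it can be seen and adjusted for. Selection on features that are not recorded cannot.

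**Conclusion.** The point holds as a weakness in the written procedure. Followed as it stands, section 4.4 leaves allocation in an open trial open to being foreseen by those who decide entry. The resulting bias cannot be sized from the document, and nothing shows that it would occur. It can be only partly repaired in analysis, and a rule that turns on one boy leaves little room for it.

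The silence on blocks and on separate lists is a lesser gap. The 19% chance of exactly 15:15 rests on a single list balanced 35:35, which the plan does not state. Missing the planned split would be a small loss of precision, about 4% in variance at 18:12, and not a threat to validity. The change is worth making because it is cheap, chiefly for the sake of concealment.

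**What to change.** Change section 4.4 to state the following.

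- Separate 1:1 permuted-block lists are generated for Group I and Group II. Block sizes are not disclosed to investigators and are chosen so that the lists close at 30 and 40. Blocks of 4 and 6 in random order would do this: 3 × 6 + 3 × 4 = 30 and 4 × 6 + 4 × 4 = 40.
- The lists are generated and held by someone outside recruitment, for example the trial-support unit already named as monitor on the title page. The same holder adds blocks if boys are replaced or the futility look increases the numbers.
- The treatment is released only after consent and eligibility are recorded, either by one central holder or from sealed, opaque, numbered envelopes with a set for each hospital.

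The cost is two short lists and a small administrative step per boy. If envelopes are kept at each of the two hospitals, each group needs a set at each hospital. Unfinished blocks may then miss the exact 15:15 and 20:20 splits slightly; release by one central holder avoids this.
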